4.3 Ordering

Ordered in Radiology Information System (RIS), address per above.

4.4 Agent Accountability

RIS is password-protected and part of the electronic medical records.

5. IMAGING SPECIFICS

5.1 Modality or Modalities to be used

PET/MRI

5.2 Details of Imaging (ie, dynamic, static, number of scans, etc)

A localizer MRI scan will be performed at 45 minutes after injection of $140 \pm 20\%$ mBq of ^{68}Ga -RM2 (or 3 to 7 mCi of ^{68}Ga -PSMA11, depending on randomization) to define the table positions. After

correct positioning of the spatial acquisition windows is ensured, the combined PET/MRI acquisition will be initiated with 3 to 5 table positions at a 2 to 4 min acquisition time per table position. A volumetric T1 acquisition with fat-water separation and motion correction to enable free-breathing will be obtained at each table position and used for the generation of attenuation maps and for anatomic allocation of the PET results. Simultaneously with the start of the T1 MRI sequence, the PET acquisition will start at the same table position, thus ensuring optimal temporal and regional correspondence between MRI and PET data. The PET acquisition time will be 4 min per table position, taking delayed acquisition times and radioactive decay into account. As the T1 will take less than 4 minutes, a rapid diffusion weighted MRI will also be performed. After completion of the PET acquisition, the table will be moved to the next table position and the procedure will be repeated. Upon completion of the PET acquisition for all stations, volumetric post-contrast T1- and T2-weighted MR images may be obtained at multiple stations as needed.

A localizer MRI scan will be performed at 45 minutes after injection of 3 to 7 mCi of ^{68}Ga -PSMA11 (or ^{68}Ga -RM2, depending on randomization) to define the table positions. After correct positioning of the spatial acquisition windows is ensured, the combined PET/MRI acquisition will be initiated with 3 to 5 table positions at a 2 to 4 min acquisition time per table position. Only MR sequences required for attenuation correction of PET data will be acquired.

Participants will be randomized to have ^{68}Ga -RM2 first followed by ^{68}Ga -PSMA11 within 2 weeks or ^{68}Ga -PSMA11 first followed by ^{68}Ga -RM2 within 2 weeks (50/50 chance for each schedule).

The above will be repeated approximately 6 months after HDR local treatment.

5.3 Image interpretation

The PET/MRI scans will be interpreted by ABNM certified Nuclear Medicine physicians and ABR certified Radiologists. Drs [name], [name], [name] and [name] have significant clinical experience and will be blinded to the participants' medical history and the results of other imaging modalities. Consensus read will be obtained for each scan. Each lesion will be tabulated and a comparison of lesion detection by each tracer will be conducted.

The study team will communicate the results of the scans to the referring (treating) physicians.

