6.3 Follow-up

Active subject participation ends after the 24 to 72 hour Safety Follow-up after the 2nd post-therapy scan. Investigators will follow subjects by chart review for 12 months post-scan to record any standard of care biopsies or imaging results. The investigators will assist with identification of lesions that can be biopsied, based on ⁶⁸Ga-RM2 and/or ⁶⁸Ga-PSMA11 PET/MRI findings.

If a subject transfers clinical care outside of Stanford Healthcare during the chart review clinical follow-up period, investigators will request permission to contact the treating physician.

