7. STUDY CALENDAR

	Pre-Study	Scan Date	24 to 72 hours Post-Scan	12 months
Informed consent	X			
Demographics	X			
Medical history	X			
⁶⁸ Ga-RM2		X ^a		
⁶⁸ Ga-PSMA11 (\geq 3 days and \leq 2 weeks)		X ^a		
Follow-up call to participant (24 to 72 hours)			X	
Chart review ^b				X

a: Subjects will undergo either ⁶⁸Ga-RM2 PET/MRI followed within 2 weeks by ⁶⁸Ga-PSMA11 PET/MRI, or ⁶⁸Ga-PSMA11 PET/MRI followed within 2 weeks by ⁶⁸Ga-RM2 PET/MRI. After the 1st scan, the 2nd scan will only occur after the follow-up with the patient for the 1st scan, and after a minimum of 3 days have elapsed. This will be repeated approximately 6 months after HDR local treatment, prior to standard of care biopsy to evaluate for residual disease in the prostate.

b: Subjects will be followed by chart review for 24 months from initial scan date. If a subject transfers clinical care from Stanford HealthCare, investigators may request records from the treating physician.

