Because there may be multiple lesions per-patient and an indefinite number of non-lesions, the primary analysis will be per-region. Each of the 12 regions will have gold-standard positive or negative information, as well as imaging positive or negative assessments. Predictive accuracy of PI-RADS composite score (mpMRI) and SUV_{\max} PET uptake values will be assessed by ROC analysis using univariable logistic regression for the presence of PC. Areas under the entire ROC curve, and partial area at fixed 90% specificity will be compared. Additional benefit of the other modalities over mpMRI alone will be tested by a multivariable logistic regression. All analyses will be adjusted for clustering within patient.

Statistical Power and Sample Size: Based on our clinical experience at Stanford, we expect an average of 2 PC-positive regions and 10 PC-negative regions per patient. Assuming mpMRI has sensitivity of 80% and specificity of 80-90% [91], a sample size of 1200 regions with 20% prevalence will provide 90% power at 5% error to demonstrate non-inferiority of a PET sensitivity of 90% at 80-90% specificity [62, 92, 93].

The per-lesion analysis will depend on the number of lesions found but will be similar. We will also explore whether specific imaging findings are especially accurate in detection of specific subtypes of PC or prostate regions (i.e., peripheral versus transitional zones). It may also be the case that

predictive failures in imaging may be associated with a particular subtype. Given the small sample, we acknowledge that this analysis will be exploratory.

10.2 Aim 2

Participants: Those enrolled in Aim 1.

Design: Patients will be scanned with both ⁶⁸Ga-RM2 PET/MRI and ⁶⁸Ga-PSMA-11 PET/MRI at six months after initiation of therapy. MRI and PET images will each be evaluated separately.

Outcome measures: Changes in MRI features and/or changes in radiopharmaceutical uptake in lesions will be recorded for each modality in each patient. Gold standard of response to treatment and of PFS will be based on standard clinical follow-up (PSA, imaging, tissue diagnosis including IHC stains for GRPr and PSMA)

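### Aim 2: study PET results reach treating physicians and guide biopsies, and no rule separates scan-prompted findings from the response and PFS outcomes that PET is meant to predict

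*Combined protocol and SAP*

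**What the plan says.** Section 10.2 hypothesises that the change in tracer uptake from baseline to 6 months predicts treatment response (primary) and PFS (secondary) better than the change in MRI. Response is analysed by logistic regression and McNemar tests. PFS is analysed by a log-rank test at a median split and by Cox regression.

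The plan's statements on how scan results and outcomes meet are these:

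- **Release (5.3).** "The study team will communicate the results of the scans to the referring (treating) physicians". No tracer or time point is excepted.
- **Biopsy targets (6.3).** "The investigators will assist with identification of lesions that can be biopsied, based on ⁶⁸Ga-RM2 and/or ⁶⁸Ga-PSMA11 PET/MRI findings".
- **Order (2.5 and the section 7 footnote).** The repeat scans take place about 6 months after treatment, "prior to standard of care biopsy to evaluate for residual disease in the prostate".
- **Outcome (10.2, Outcome measures).** "Gold standard of response to treatment and of PFS will be based on standard clinical follow-up (PSA, imaging, tissue diagnosis", the tissue part including the receptor stains.
- **Collection (6.3).** "Investigators will follow subjects by chart review for 12 months post-scan to record any standard of care biopsies or imaging results". The section 7 footnote gives a different length: "Subjects will be followed by chart review for 24 months from initial scan date". These two must be reconciled, but that is a separate point.
- **Blinding (5.3).** The image readers "will be blinded to the participants' medical history and the results of other imaging modalities". Section 10.1 also blinds readers. No blinding is stated for whoever assigns response or progression.

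The text defines no progression event, sets no work-up schedule independent of the study scans, and gives no rule for findings that those scans prompted.

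**The concern.** A predictor should not help to produce the outcome it is tested against. Here the PET result can be known to the physician who decides on further work-up and can steer where the needle goes. What that work-up finds is then counted as non-response or progression. If suspicious uptake leads to more, sooner or better-aimed biopsies, disease is recorded more often in those men even when true progression is the same, and PET looks more predictive than it is. Reader blinding protects the scan interpretation, not the outcome.

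Section 2.1 (Efficacy assessment) makes this more relevant. It calls PSA a poor measure of efficacy after HDR and gives the Phoenix criterion about 65% sensitivity and 77% specificity for clinical recurrence. Outcome assessment therefore leans on imaging and tissue, the two components that a released scan can influence. Without a record of what prompted each biopsy or scan, a positive Aim 2 result could not be told apart from scan-driven detection.

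**Working it through.** **1. Which outcome components are exposed?**

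- PSA: a PET read does not change the value, so this part is least exposed.
- Imaging: later clinical imaging can be prompted by a released study result. Whether the study reads themselves count is not stated.
- Tissue at about 6 months: the biopsy is described as standard of care and not as conditional on PET. Its targets can still be PET-informed, because the scan comes first.
- Tissue after that: both the decision to biopsy and the target can follow from the study scan.

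**2. How many PFS events carry the result?** Section 10.2 expects 20% of responders to progress by two years. It gives about 75 responders in one place and median-split groups of about 40 each (80) in another.

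- 0.20 × 75 = 15 and 0.20 × 80 = 16 events.

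The plan's own figure is 90% power for a hazard ratio (HR) of 2.5 at one-sided 5%. By Schoenfeld's formula this needs 4 × (1.645 + 1.282)² / (ln 2.5)² ≈ 41 events. With d events, power = Φ(½√d × ln 2.5 − 1.645), which is 55% at d = 15 and 57% at d = 16. The stated 90% is not reproduced. That shortfall is a separate matter; what counts here is how few events there are.

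**3. How far could a few diagnoses move it?** Illustration, assuming constant hazards and complete 24-month follow-up. Sixteen events split evenly are 8/40 v 8/40, so HR = 1. Suppose work-up prompted by study scans adds three or four recorded events in one group only (assumed numbers):

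- 11/40 v 8/40: ln(0.725)/ln(0.80) = 1.44
- 12/40 v 8/40: ln(0.70)/ln(0.80) = 1.60

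**4. Can the size of the bias be derived?** Take true progression as 20% in both groups, so there is no true association, and let only detection differ. Apparent HR = ln(1 − recorded proportion, PET-suspicious group) / ln(1 − recorded proportion, other group). The 65% and 77% come from section 2.1; the 90% to 100% is assumed.

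| Assumption | Other group | PET-suspicious group | Apparent HR |
|---|---|---|---|
| Detection 65% v 90%, no false positives | 0.20 × 0.65 = 13.0% | 0.20 × 0.90 = 18.0% | 1.43 |
| Detection 65% v 100%, no false positives | 13.0% | 20.0% | 1.60 |
| As above, plus 23% false positives in both groups (0.80 × 0.23 = 18.4%) | 31.4% | 36.4% to 38.4% | 1.20 to 1.29 |
| Biopsy replaces the PSA call in the suspicious group (100% detection, no false positives) | 31.4% | 20.0% | ln(0.80)/ln(0.686) = 0.59 |

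A simulation of the planned log-rank test (40 v 40, 24 months, exponential times, true HR 1, 6,000 runs per scenario) without false positives gave one-sided rejection of about 10%, 15% and 21% for detection of 80%, 90% and 100% against 65%, instead of 5%.

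These rows compare PET-suspicious men with the rest. The planned test splits at the median change in uptake, which is not PET positivity, so the detection contrast would probably be diluted. Size, and under the last row even direction, depend on inputs the documents do not give.

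**The case against.** A reader might go further than the text allows in four ways.

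- **That only PET-positive men are biopsied while the others wait for PSA.** The plan describes a standard-of-care biopsy after the 6-month scans with no PET condition. For response, the primary Aim 2 hypothesis, this stands as a real limit on differential verification. It does not cover PET-informed targeting or later PFS work-up, and 10.2 does not say that this biopsy is what defines response.
- **That the study PET read is itself part of the outcome.** The gold standard is standard clinical follow-up, and chart review records standard-of-care results, while both tracers are investigational. The natural reading may already leave the study read out. This is an ambiguity to close, not an established error.
- **That the bias favours PET over MRI.** The released results are PET/MRI, so MRI findings can prompt the same work-up. An advantage to PET arises only where PET prompts more of it, which cannot be shown from the documents.
- **That the spurious hazard ratio is 1.4 to 1.6.** The arithmetic is right, but it uses the 65% sensitivity without the 77% specificity quoted beside it, assumes the 90% to 100%, and does not model the median split.

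It can also be said that the primary endpoints in 2.5 and the registered outcomes in 10.3 count participants with an assessment obtained, which this bias does not touch. That is correct; the point concerns the Aim 2 hypotheses, and PFS is the secondary one.

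None of this supplies a rule for scan-prompted findings.

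**Conclusion.** The concern holds as a gap in the Aim 2 plan. Release of results, PET-guided biopsy targets, PET before biopsy, and outcomes taken from the resulting care are all in the text, and no safeguard is stated on the outcome side. As written, the plan lets the test under study influence its own reference standard, which can inflate PET's apparent prediction. Exposure is smaller for response than for PFS.

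No size can be put on the bias. What the documents do support is that the PFS result would rest on about 15 to 16 events, so a handful of scan-prompted diagnoses could matter. The hazard ratios and error rates above are illustrations under assumed detection rates.

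Nor do the documents support making the main analysis drop events found through PET-directed work-up. That would remove genuine progression selectively from men with suspicious scans and lean toward the null. This is a cheap improvement to the plan, not a reason to redesign the study.

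**What to change.** In section 10.2:

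1. State that study PET and study MRI reads do not count as the imaging component of response or PFS.
2. Add a CRF field, completed prospectively, for what prompted each biopsy or scan: scheduled, PSA, symptoms, study PET or study MRI. This may not be recoverable from charts later.
3. Keep all events in the main analysis. Prespecify a sensitivity analysis that excludes events prompted only by study PET/MRI, and interpret a positive Aim 2 result in light of both.
4. Where feasible with existing staff, have response and progression assigned without access to the study PET reads.

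The cost is some wording, one CRF field and one extra analysis. Item 4 is harder than it sounds: results go to treating physicians and the ordering system is part of the medical record (4.3, 4.4), so someone else would probably have to prepare a chart extract. The sensitivity analysis will be imprecise with so few events and may itself lean toward the null, because some excluded events will be real. No change to the release of results or to clinical care is proposed.

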6. STUDY PROCEDURES

6.1 Pre-Study

Potential subjects will be referred by treating physicians for participation in this imaging study. The following procedures will occur pre-study:

- Review of eligibility criteria
- Obtain informed consent
- Collect demographics
- Review medical history, including any concomitant medication.

6.2 Imaging Days

Subjects will undergo 2 separate clinic visits not less than 3 days apart for imaging before therapy and two separate clinic visits for imaging after therapy. After the 1st scan, the 2nd scan will only occur after the follow-up with the patient for the 1st scan, and after a minimum of 3 days have elapsed. On each imaging day, subjects will receive an intravenous (IV) injection of investigational

imaging agent (⁶⁸Ga-RM2 or ⁶⁸Ga-PSMA11) and undergo PET/MRI image collection as described above.

6.3 Follow-up

Active subject participation ends after the 24 to 72 hour Safety Follow-up after the 2nd post-therapy scan. Investigators will follow subjects by chart review for 12 months post-scan to record any standard of care biopsies or imaging results. The investigators will assist with identification of lesions that can be biopsied, based on ⁶⁸Ga-RM2 and/or ⁶⁸Ga-PSMA11 PET/MRI findings.

If a subject transfers clinical care outside of Stanford Healthcare during the chart review clinical follow-up period, investigators will request permission to contact the treating physician.

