1. OBJECTIVE

Specific Aims

Aim 1: ^{68}Ga -RM2 PET/MRI and ^{68}Ga PSMA-11 PET/MRI detection of PC. We will investigate the performance of the new GRPr-binding PET radiopharmaceutical, ^{68}Ga -RM2, and compare it to the currently most widely investigated (but not FDA-approved) PC PET radiopharmaceutical, ^{68}Ga PSMA-11, as well as to mpMRI acquired during PET/MRI for the localization and staging of low-risk and intermediate-risk PC. New lesions identified on PET/MRI and not known from prior systematic prostate biopsy will be confirmed by targeted biopsy and GRPr and PSMA status will be evaluated with specific immunohistochemical stains [1, 2].

Aim 2: ^{68}Ga -RM2 PET/MRI and ^{68}Ga PSMA-11 PET/MRI prediction of PFS after local targeted therapy for PC. We will investigate if the combination of the GRPr-binding PET imaging agent, ^{68}Ga -RM2, and the most widely investigated (but not FDA-approved) PSMA-binding PET imaging agent, ^{68}Ga PSMA-11, together with mpMRI can predict PFS after local targeted therapy. We will determine if ^{68}Ga -RM2 PET/MRI and ^{68}Ga -PSMA-11 PET/MRI assessment at 6-months follow-up will predict PFS at 24 months based on standard clinical follow-up (PSA, imaging, tissue diagnosis).

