5. Approximately 45 to 60 minutes after the radiopharmaceutical IV administration, data acquisition will begin in the pelvic region and move toward the head. First, localizer MRI scans will be performed to define the table positions. After correct positioning of the spatial acquisition windows is ensured, the combined PET/MRI acquisition will be initiated with 3 to 5 table positions at a 2 to 4 minute acquisition time per table position. Only MR sequences required for attenuation correction of PET data will be acquired.
6. Vital signs (heart rate, blood pressure) will be recorded again at the completion of the study.
7. Participants will be contacted at 24 to 72 hours following the scan in order to capture potential occurring Adverse Events.

The above will be repeated approximately 6 months after HIFU or HDR local treatment, prior to standard of care biopsy to evaluate for residual disease in the prostate.

Objectives of the Study

Primary Objectives

- To demonstrate that ⁶⁸Ga-RM2 and ⁶⁸Ga-PSMA-11 PET/MRI can detect additional cancers over mpMRI.
- To demonstrate that ⁶⁸Ga-RM2 and ⁶⁸Ga-PSMA-11 PET/MRI can assess changes in response to treatment and predict PFS at 24 months.

Secondary Objective

- None

Endpoints

Primary Endpoints

- Number of participants with assessable additional prostate cancer lesions over mpMRI
- Number of participants with assessable pre- and post-treatment uptake in response to HIFU or HDR local therapy

Secondary Endpoint

- None

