3.4 Study Timeline

3.4.1 Primary Completion:

The study will reach primary completion 24 months from the time the last subject completes the first scan.

3.4.2 Study Completion:

The study will reach study completion 84 months from the time the study opens to accrual.

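### Chart review lasts 12 months in Section 6.3 and the calendar column but 24 months in the calendar footnote; under 6.3, PFS at 24 months would generally not be fully observed, and PSA is not named

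*Combined protocol and SAP*

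**What the plan says.** Three places set the length of chart review, and they disagree.

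- Section 6.3: "Investigators will follow subjects by chart review for 12 months post-scan to record any standard of care biopsies or imaging results". The sentence before it reads: "Active subject participation ends after the 24 to 72 hour Safety Follow-up after the 2nd post-therapy scan".
- Section 7, calendar grid: the chart-review mark stands in the 12-month column.
- Section 7, footnote b, attached to that row: "Subjects will be followed by chart review for 24 months from initial scan date".

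The outcome that depends on this follow-up is described elsewhere. A primary objective in Section 2.5 is that PET/MRI "can assess changes in response to treatment and predict PFS at 24 months". Section 10.2 gives the data sources: "Gold standard of response to treatment and of PFS will be based on standard clinical follow-up (PSA, imaging, tissue diagnosis", with IHC stains as part of the tissue diagnosis. Aim 2 in Section 1 names the same three sources. On timing, Section 3.4.1 says: "The study will reach primary completion 24 months from the time the last subject completes the first scan". Section 3.4.2 puts study completion at 84 months from opening, Section 10.3 gives 84 months for the second primary outcome, and Section 10.4 expects 20 patients a year for five years.

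**The concern.** Once active participation ends, chart review is the only source of outcome data that the plan describes, so its length decides whether month 24 is observed. Staff who follow Section 6.3 or the calendar column would stop at 12 months; staff who follow the footnote would go on to 24. Section 6.3 does not say which scan starts its 12 months, and no section defines the time origin for PFS or gives the interval from first scan to HDR brachytherapy.

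Section 6.3 lists biopsies and imaging as the items to record. It does not exclude PSA, but it does not ask for it either, although PSA is one of the three bases for PFS. At stake are the number of progression events available for the log-rank and Cox analyses in Section 10.2, and whether 24-month status can be established for each patient.

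**Working it through.** **Which rule fits the plan's own timeline.** Accrual is 100 / 20 per year = 5 years = 60 months. Adding 24 months for the last patient gives 60 + 24 = 84, the stated figure, with no slack. Footnote b fits this exactly and matches Section 3.4.1. The 84 months alone does not rule out 6.3, because a shorter review also fits inside it. The 24-month objective, footnote b and Section 3.4.1 together make the 12-month texts the outliers.

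**Where review ends.** Let *d* be the months from first scan to HDR. The plan does not give it; I assume 0.5 to 3. Post-therapy imaging is about 6 months after HDR, with the second scan up to 0.5 month after the first (Sections 2.5 and 7).

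| Rule | End, months after HDR | End, months after first scan |
|---|---|---|
| 6.3, from 2nd post-therapy scan | 6 + (0 to 0.5) + 12 = 18 to 18.5 | 18 + 0.5 = 18.5 up to 18.5 + 3 = 21.5 |
| 6.3, from first scan | 12 − *d* = 11.5 to 9 | 12 |
| Footnote b | 24 − *d* = 23.5 to 21 | 24 |

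Section 6.3 reaches month 24 only if all three conditions hold: the clock starts at the post-therapy scan, PFS is counted from the first scan, and *d* is at least 24 − 18.5 = 5.5 to 24 − 18 = 6 months.

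**Events observed.** Inputs from Section 10.2 are 20% of responders progressing by two years and about 75 responders. I add a constant hazard, which the plan does not state: *h* = −ln(0.8)/24 per month, and events by month *t* = 75 × (1 − exp(−*ht*)).

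| *t* (months) | Events | Share of 15.0 |
|---|---|---|
| 9 | 6.0 | 40% |
| 11.5 | 7.6 | 51% |
| 12 | 7.9 | 53% |
| 18 | 11.6 | 77% |
| 18.5 | 11.9 | 79% |
| 21 | 13.3 | 89% |
| 21.5 | 13.6 | 91% |
| 23.5 | 14.7 | 98% |
| 24 | 15.0 | 100% |

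By rule and PFS origin:

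- 6.3 from the post-therapy scan: 11.6 to 11.9 events with HDR as origin; 11.9 to 13.6 with the first scan as origin.
- 6.3 from the first scan: 7.9 with the first scan as origin; 7.6 down to 6.0 with HDR as origin.
- Footnote b: all 15.0 with the first scan as origin; 14.7 down to 13.3 with HDR as origin.

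The shares do not depend on the number of responders. With 70 or 80 responders, the 24-month total is 14.0 or 16.0.

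**Sensitivity.** The predictor is measured at 6 months, so only later events may count. With HDR as origin, events after month 6 = 75 × (exp(−6*h*) − exp(−*ht*)). This gives 10.9 by month 24, against 7.5 to 7.8 by months 18 to 18.5 (69 to 71%) and at most 3.8 by month 12 (35%).

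**The case against.** The best reply is that this is a wording conflict with a limited effect. Footnote b sits on the chart-review row, so calendar users see 24 months. The listed primary endpoints are counts, for instance "Number of participants with assessable pre- and post-treatment uptake in response to HIFU or HDR local therapy"; Section 10.2 labels the PFS hypothesis secondary; and log-rank and Cox methods accept censored data. All of that is right and limits the damage. It does not remove the conflict, because 6.3 is the section that instructs staff and fixed-time status at 24 months cannot be established for patients whose review stops earlier.

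A second reply is that standard-of-care records would still exist and could be abstracted later. They might, but nothing in 6.3 tells anyone to do so, and patients who transfer care are harder to trace.

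A third concerns PSA: Sections 1 and 10.2 already make it part of PFS, and the list in 6.3 may be meant for lesion verification. That is possible. The point is only that the section governing data collection does not name it.

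A fourth is that shorter review is not what limits the PFS comparison. Section 10.2 claims 90% power for a hazard ratio of 2.5 at one-sided 5%. The Schoenfeld formula needs 4 × (1.645 + 1.282)² / (ln 2.5)² ≈ 41 events, whereas two groups of 40 with 20% progression give 16. One-sided power is then about 57% at 24 months, 49% at 18 (12.3 events) and 38% at 12 (8.4 events). This stands: the comparison is short of events under either rule. It is a separate matter, and with so few events each one lost costs more.

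Finally, the 12-months-from-first-scan reading is the weaker of the two, since the sentence before names the second post-therapy scan. The lowest event counts should be read in that light.

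**Conclusion.** The contradiction is certain: 12 months in Section 6.3 and the calendar column, 24 months in footnote b. If 6.3 is followed, collection generally stops before the 24-month horizon of a stated primary objective. On the more natural reading, with post-scan meaning after the second post-therapy scan, the loss is about 15.0 − 13.6 = 1.4 to 15.0 − 11.6 = 3.4 of 15 expected events. On the first-scan reading it is about 15.0 − 7.9 = 7.1 to 15.0 − 6.0 = 9.0.

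The counts are indicative. They rest on the assumed constant hazard and the assumed 0.5 to 3 months from first scan to HDR, and they depend on a PFS origin that the plan leaves open. The conflict should be fixed, but it does not touch the count-type primary endpoints.

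**What to change.** 1. Change Section 6.3 and the calendar column to agree with footnote b, so that chart review covers at least 24 months from a stated PFS time origin for every participant.
2. State that origin. If it is HDR, extend footnote b by the scan-to-HDR interval. Then check that Sections 3.4.1 and 3.4.2 still allow 24 months for the last participants enrolled: 20/12 × *d* = 0.8 to 5.0, or about 1 to 5 of 100, for *d* = 0.5 to 3 months.
3. Add PSA values and their dates to the items that 6.3 says are recorded.

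The cost is a protocol modification with IRB approval (Section 9.1) and more chart review, with no new visits or procedures. Extra review per patient would be:

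- against 6.3 read from the post-therapy scan: 5.5 to 6 months if the origin is HDR, or 2.5 to 5.5 if it is the first scan;
- against 6.3 read from the first scan: 12 months, plus *d* if the origin is HDR;
- against footnote b: none, or only *d* if the origin is HDR.

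The consent text is not available, so whether it would need to change cannot be judged.
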